6.4.3 Data Collected at Study Completion

For patients who complete the observation period, the study completion visit should be documented.

~~Please see Appendix 2 for the data collection overview at the study completion visit.~~

6.4.4 Safety Data Collection

Clinical AEs, serious and non-serious, will be recorded in the eCRF during the total observation period, with physician's assessment of severity (mild, moderate, severe or in oncology studies using the National Cancer Institute [NCI] Common Terminology Criteria for Adverse Events [CTCAE]) and relationship to therapy (i.e., related or unrelated) as described in Appendix 3.

6.5 PATIENT, STUDY AND SITE DISCONTINUATION

6.5.1 Patient Discontinuation

Patients have the right at any time and for any reason to withdraw their consent that their data are collected and used for the study. Reasons for discontinuation of treatment with the medicinal product or withdrawal from the study may include, but are not limited to, the following:

- Any medical condition that the investigator or Sponsor determines may jeopardize the patient's safety if he or she continues to receive study treatment;
- Investigator or Sponsor determines it is in the best interest of the patient;
- Pregnancy;
- Symptomatic deterioration attributed to disease progression;
- Intolerable toxicity related to Obinutuzumab, as determined by the investigator to be unacceptable given the individual patient's potential response to therapy and severity of the event;
- Any medical condition that may jeopardize the patient's safety if he or she continues on study treatment;
- Confirmed disease progression per investigator assessment;
- Patient withdrawal of consent at any time;
- Patient is lost to follow-up.

6.5.2 Discontinuation from Treatment with Studied Medicinal Product

The decision for discontinuation from treatment lies with the treating physician in agreement with the patient's decision and is not regulated by this protocol.

The primary reason for early treatment discontinuation should be documented on the appropriate eCRF page. Every effort should be made to obtain information on patients who discontinue treatment.

Patients who discontinue treatment for reasons other than disease progression should continue to have its data collected for radiological assessment and minimal residual disease as collected by clinical practice until disease progression. Data of new anti-cancer therapy within 3.5 years after first line and survival status should also be collected as available.

6.5.3 Withdrawal from Study

Every effort should be made to obtain information on patients who withdraw from the study. The primary reason for withdrawal from the study should be documented on the appropriate eCRF page. Patients will not be followed for any reason after consent has been withdrawn. Patients who withdraw from the study will not be replaced.

6.5.4 Study and Site Discontinuation

The sponsor has the right to terminate this study at any time. Reasons for terminating the study may include, but are not limited to, the following:

- The incidence or severity of adverse events in this or other studies indicates a potential health hazard to patients;
- Patient enrolment is unsatisfactory.

The sponsor will notify the physician if the study is placed on hold, or if decided to discontinue the study.

The sponsor has the right to replace a site at any time. Reasons for replacing a site may include, but are not limited to, the following:

- Excessively slow recruitment
- Poor protocol adherence
- Inaccurate or incomplete data recording
- Non-compliance with the Guidelines for Good Pharmacoepidemiological Practices (GPP) or any other pertinent local law or guideline

6.6 DATA MANAGEMENT

6.6.1 Data Quality Assurance

A contract research organization (CRO) will be responsible for the data management of this study, including quality checking of the data. Data entered manually will be collected via electronic data capture (EDC). Sites will be responsible for data entry into the EDC

system. In the event of discrepant data, site will be request data to clarify the discrepancy in the EDC system.

The contract research organization (CRO) Data Management will identify and implement the most effective data acquisition and management strategy for the clinical trial protocol and deliver datasets which support the protocol objectives. The CRO will produce eCRF specifications for the study based on their own templates including quality checking to be performed on the data.

Patient data will be entered into the eCRF and combined with data provided from other sources (e.g., ePRO data) in a validated data system. Clinical data management will be performed in accordance with applicable CRO standards and data cleaning procedures with the objective of removing errors and inconsistencies in the data which would otherwise impact on the analysis and reporting objectives, or the credibility of the Clinical Study Report. Adverse events and concomitant medications terms will be coded using validated dictionaries.

The eCRFs and correction documentation will be maintained in the EDC system audit trail. System backups for data stored at the CRO and records retention for the study data will be consistent with the CRO standard procedures.

The study data should be verified by the Clinical Research Associate (CRA), i.e. the study monitor, with the original data, thereafter all the records and clinical records of the subjects could be accessible. The investigator should allow the access to patient clinical records and the original data should be available for all the study duration. Also the subjects and parents/legal representatives should allow the access to their own clinical records; such condition is cleared and authorized when the subjects supply their authorization for the participation to the clinical study.

To ensure instrument validity and that data standards meet health authority requirements, questionnaires scheduled for administration during a clinic visit will be completed in their entirety by the patient prior to the performance of non-PRO assessments and the administration of study treatment (where applicable).

Patients will use an electronic PRO (ePRO) device to capture PRO data on the same day of clinic visits. ePRO data collection will be performed by the patients through a dedicated app installed on smartphone. The data will be transmitted via a pre-specified transmission method (e.g., web or wireless) automatically after entry to a centralized database at the ePRO vendor. In case application in smartphone cannot be used, ePRO data might be completed by patients directly in web-application at a computer available at site. The data can be accessed by the appropriate sponsor study personnel securely via the Internet.

In case patient is not able to complete the electronic questionnaires, e.g due to technical issues, the PRO data will be completed by patient in paper records and later transferred into the electronic system by site staff.

6.6.2 Electronic Case Report Forms

Clinical data will be captured using a study specific eCRF using a validated and Code of Federal Regulations (CFR) Part 11 compliant electronic data capture (EDC) system. Sites will receive training and have access to a manual for appropriate eCRF completion.

All eCRFs should be completed by designated trained site staff. eCRFs should be reviewed and electronically signed and dated by the physician or a designee.

At the end of the study, the physician will receive the data related to patients from his or her site in an electronically readable format (e.g., on a compact disc). Data must be kept with the study records. Acknowledgement of receipt of the data is required.

6.6.3 Source Data Documentation

Site Operations Representative will perform ongoing SDV as defined in the Clinical Monitoring Plan to confirm that critical protocol data (i.e., source data) entered in the CRF by authorized site personnel are accurate, complete, and verifiable from source documents.

Source documents (paper or electronic) are those in which patient data are recorded and documented for the first time. They include, but are not limited to, hospital records, clinical and office charts, laboratory notes, memoranda, PROs, evaluation checklists, pharmacy dispensing records, recorded data from automated instruments, copies of transcriptions that are certified after verification as being accurate and complete, microfiche, photographic negatives, microfilm or magnetic media, X-rays, patient files, and records kept at pharmacies, laboratories, and medico-technical departments involved in the clinical study.

Before study initiation, the types of source documents that contain study-relevant information will be clearly defined in the Clinical Monitoring Plan. The Clinical Monitoring Plan defines which kind of source data – if available from clinical routine – can be used for documentation into CRF. No additional source data creation beyond routine is allowed.

Source documents that are required to verify the validity and completeness of data entered in the CRF must not be obliterated or destroyed and must be retained per the policy for retention of records described in Section 6.8.4.

To facilitate SDV, the physicians and institutions must provide the marketing authorization holder direct access to applicable source documents and reports for

trial-related monitoring, marketing authorization holder audits, and IRB/EC review. The participating sites must also allow inspection by applicable health authorities.

6.7 STATISTICAL CONSIDERATIONS

A detailed description of the statistical methods that will be used for the primary and secondary analyses will be provided in the Statistical Analysis Plan (SAP).

The statistical analysis will be performed using the *R* system. ~~SAS System version 9.4 or higher.~~

This is not a hypothesis testing study but an exploratory study with predefined precision of estimates for key efficacy and safety parameters; there are no formal statistical hypotheses tests to be tested, and there will be no adjustments for multiplicity of endpoints or within-subgroups comparisons.

As when entering in the initial patient's treatment/pre-treatment data are collected retrospectively, missing data might occur in the retrospective period as well the distribution of missing data might be different across the participating investigational sites.

Data will be summarized using appropriate descriptive statistics. Categorical data will be presented as frequencies and percentages. For continuous data, arithmetic mean, standard deviation (STD), median, minimum, and maximum will be presented. The 95% confidence interval of the observed proportions (calculated using either the Clopper-Pearson methodology, or the Poisson distribution, for frequencies below 10%) will be provided.

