Retrospective data applicable to the study includes but not limits to the following information available before ICF signature (enrolment):

- Information regarding previous cycles performed with Obinutuzumab and chemotherapy (at least 2 cycles and no longer than 1 year of treatment)
- Safety data
- Baseline condition (before start of the treatment)
- Medical history
- Relevant laboratory exams
- Concomitant medication and procedures
- Diagnostic information
- Tumor assessments and cancer history
- Imaging exams
- Demographic Data
- Physical exams, performance status and FLIPI classification

Data will be collected as availability in source document.

Safety data will be provided as aggregate data for retrospective visits. Minimal information such as the event term, seriousness classification and reason, relationship and duration of the event will be collected as available. For prospective data collection of safety, additional variables will be collected as available, such as grade, outcome, concomitant treatment, background causality, onset and end date.

Quality of life will be evaluated by means of the EuroQol 5-Dimension Questionnaire, 5-level version (EQ-5D-5L), and of the Functional Assessment of Chronic illness Therapy-Lymphoma (FACT-Lym).

The EuroQol 5-Dimension Questionnaire, 5-level version (EQ-5D-5L) (Appendix 4), is a validated self-report health status questionnaire that is used to calculate a health status utility score for use in health economic analyses (*EuroQol Group 1990; Brooks 1996; Herdman et al. 2011*).

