6.7.1 Effectiveness Analyses

Effectiveness analysis population includes all patients who are enrolled and have received at least two cycles of Obinutuzumab.

In general, the time to endpoint will be defined as an interval between the date of enrolment (date of first visit) and date of first occurrence of the event. For patients who are event free, the censoring time will be calculated as a time interval between date of enrolment and the patient's final contact with available data concerning the event. The estimates and graphical presentation will be performed via Kaplan-Meier approach.

Logistic regression will be performed on the rate of endpoints in order to test the impact of covariates, i.e. age, sex, ECOG PS, Ann Arbor staging, FLIPI, hepatitis infection (history of past/ resolved infection or latent HBV after prophylaxis as per standard treatment guidelines), chemotherapy backbone choice, medical history and history of FL, comorbidities. The list of the covariates to be included in the multivariate models will be detailed and justified in the statistical analysis plan document.

Exploratory analysis between different medical treatments given or subgroup analysis will be performed using Cox regression model and including relevant covariates. The list of the covariates to be included in the multivariate models will be detailed and justified in the statistical analysis plan document.

Further analyses will be performed to investigate different types of bias that might be present in this type of study design, e.g. time-dependent confounding, informative censoring, informative treatment changes/discontinuations, heterogeneity of results, and how to handle missing data.

Corresponding 95% confidence intervals (CIs) will be provided for all statistical estimates.

Primary endpoint

The primary endpoint is progression of disease at 2 years (POD24).

POD24 will be analyzed according to the survival analysis methods. The quartiles with their 95% confidence interval (estimated using Kaplan-Meier methods and Greenwood's formula) will be presented. Kaplan-Meier plots with a 95% CI will be prepared. Estimates for the survivor function will be obtained by the Kaplan-Meier approach.

Moreover, the POD24 will be analyzed as binary variable. Number and percentage of patients with its 95% confidence interval for POD24 will be calculated.

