Logistic regression analysis will be performed to assess which variables are predictive of POD24. To identify factors associated with POD24, logistic regression analysis will be performed with backwards selection (removing factors with $P > 0.05$). Univariable associations between factors and POD24 will be calculated by using the Chi-square test.

In the analysis of POD24 will be excluded patients who die within 24 months from the treatment start with Obinutuzumab for reasons not related to the disease progression.

Secondary endpoints

Time-to-event outcomes (PFS at 2 and 3 years, TTNT, OS, TTLCB, duration of response, and time to response) will be analyzed according to the survival analysis methods. The quartiles with their 95% confidence interval (estimated using Kaplan-Meier methods and Greenwood's formula) will be presented. Kaplan-Meier plots with a 95% CI will be prepared. Estimates for the survivor functions for all time to event endpoints will be obtained by the Kaplan-Meier approach.

Cox regression analysis will be used to assess which variables are predictive of OS as well as to evaluate the association between early POD and OS from a risk-defining

event, that is, survival from time of POD for early progressors or from 2 years after diagnosis.

Response rates (ORR, CR, CR30 and rate of patients with stable disease) will be presented with the number and proportions of responders and non-responders together with two-sided, 95% Clopper-Pearson CIs.

Exploratory endpoints

All exploratory endpoints will be analyzed using descriptive statistics only.

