6.7.5 Determination of Sample size

Sample size of this clinical study is selected based on feasibility.

Sample size is justified for the primary effectiveness endpoint POD24 treated as binary variable.

A sample size of 300 evaluable patients will allow estimation of the two-sided 95% confidence interval with a width equal to 7.9% (precision 3.95%) of the POD24 when the expected percentage is equal to 13%.

The Clopper-Pearson's formula has been used for the computation.

Table 1 provides the actual width and the precision of the 95% CI and the 95% confidence limits for different percentages of POD24 when the sample size is equal to 300 evaluable patients.

Table 1 - POD24 rate and corresponding 95% Confidence Intervals

POD24 (%)	Actual Width (%)	Precision (%)	95% Clopper-Pearson Exact CI (%)
11%	7.4	3.70	From 7.7 to 15.1
13%	7.9	3.95	From 9.4 to 17.3
15%	8.4	4.20	From 11.2 to 19.6
17%	8.8	4.40	From 12.9 to 21.7

Moreover, a sample size of 300 evaluable patients will allow estimation of the two-sided 95% confidence interval with a width equal to 9.4% (precision 4.70%) of the PFS rate at 3 years (treated as binary variable) when the expected percentage is equal to 80%.

[Table 2](#) provides the actual width and the precision of the 95% CI and the 95% confidence limits for different percentages of PFS at 3 years when the sample size is equal to 300 of evaluable patients.

Table 2 - PFS rate at 3 yrs and corresponding 95% Confidence Intervals

PFS (%)	Actual Width (%)	Precision (%)	95% Clopper-Pearson Exact CI (%)
70%	10.7	5.35	From 64.5 to 75.1
75%	10.1	5.05	From 69.7 to 79.8
80%	9.4	4.70	From 75.0 to 84.4
85%	8.4	4.20	From 80.4 to 88.8
90%	7.1	3.55	From 86.0 to 93.2

Notes: From Gallium trial, PFS at 2 years has been estimated equal to 90% while PFS rate at 3 years to 80%.

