3.6 HANDLING OF MISSING DATA

There will be no missing value handling mechanisms and missing data will not be imputed.

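### The SAP drops the missing-data work that the protocol promised, so the multivariable predictor models would by default discard patients with known outcomes who lack a single baseline factor

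*Protocol*

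**What the plan says.** **Models.** Protocol 6.7.1 and SAP 3.2 list nine covariates for logistic regression: age, sex, ECOG PS, Ann Arbor stage, FLIPI, hepatitis history, chemotherapy backbone, medical and FL history (one item or two), and comorbidities. For the primary endpoint, "To identify factors associated with POD24, logistic regression analysis will be performed with backwards selection" at P > 0.05, alongside univariable chi-square tests. Cox models are planned for predictors of OS (SAP 3.2.2) and for treatment and subgroup comparisons (SAP 3.2).

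**Data.** Patients enrol after at least two cycles, so pre-treatment data are collected retrospectively (SAP 2.2). Protocol 6.4.2 says of them: "Data will be collected as availability in source document". Protocol 6.7 expects that "missing data might occur in the retrospective period as well the distribution of missing data might be different across the participating investigational sites", and SAP 3.7 repeats this as a limitation.

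**Missing values.** Protocol 6.7.1 commits to further analyses of several types of bias and of the treatment of missing values. It also says that the SAP will set out and justify the covariate list for the multivariable models. SAP 3.6 reads: "There will be no missing value handling mechanisms and missing data will not be imputed". SAP 3.4 plans no sensitivity analyses. SAP 3.2 repeats the protocol's list without a justification or a final model.

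**The concern.** A standard logistic or Cox fit with no missing-data handling omits any patient with a blank in any covariate in the model. The SAP does not use the term complete-case analysis, but that is what its rule produces. A patient whose POD24 status is known leaves the starting model for one blank field, even in a factor that backward elimination later removes. The SAP does not say whether such patients return when the model is refitted.

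The POD24 model is expected to rest on about 39 events, so each discarded event matters. The odds ratios become less precise. The modelled cohort differs from the one that gives the reported POD24 rate, probably with fewer patients from poorly documented sites. Bias is also possible if completeness depends on both outcome and factors. Nothing in the plan would show any of this.

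**Working it through.** **1. The plan's own figure.** Protocol 6.7.5 uses 300 evaluable patients and POD24 of 13%, which gives 0.13 × 300 = 39 events. The exact limits are the 2.5% quantile of Beta(39, 262) and the 97.5% quantile of Beta(40, 261), that is 9.41% and 17.34%. The width of 7.93% reproduces the stated 7.9%. This interval uses no covariates.

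**2. Events per factor with complete data.** 39 / 9 = 4.3 (39 / 10 = 3.9 if medical history and FL history count separately).

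**3. Complete cases.** Let k factors each be missing independently with probability m. The expected number retained is 300 × (1 − m)^k, and expected events are 39 × (1 − m)^k. The documents give no m, so the values below are assumptions. Six incomplete factors represents age, sex and backbone always being known.

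| m | k = 9: patients (events) | k = 6: patients (events) |
|---|---|---|
| 2% | 250 (33) | 266 (35) |
| 5% | 189 (25) | 221 (29) |
| 10% | 116 (15) | 159 (21) |

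For example, 0.95^9 = 0.630 and 0.630 × 300 = 189. Events per factor across the nine candidates at 5% are 24.6 / 9 = 2.7 (k = 9) or 28.7 / 9 = 3.2 (k = 6).

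**4. Power.** The documents state no effect size or prevalence for predictors. The assumptions are one true binary factor with odds ratio 2.5 and 40% prevalence, nine independent factors, overall POD24 of 13%, two-sided 5%, and the full logistic model simulated without the selection step.

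| m | k = 9 | k = 6 |
|---|---|---|
| 0 | about 75% | about 75% |
| 2% | 67% | 71% |
| 5% | 56% | 60% |
| 10% | 36% | 51% |

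A fresh simulation of 3,000 trials per setting gave 66% and 70% at 2%, 55% and 61% at 5%, and 37% and 48% at 10%, so the table is good to about three points.

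A two-proportion formula at 50% prevalence gives the same pattern for nine factors:
- odds ratio 2.5: 73% with full data, then 69%, 64%, 53% and 35% at 1%, 2%, 5% and 10% missing;
- odds ratio 2.0: 50% with full data, then 34% at 5% and 23% at 10%;
- odds ratio 3.0: 85% with full data, then 67% at 5% and 46% at 10%.

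Simulating backward selection itself (odds ratio 2.5, 50% prevalence, 600 runs per setting) gives 73%, 70%, 48% and 30% at 0, 2%, 5% and 10%.

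**5. Clustered missingness.** Suppose all missingness falls in 20% of patients (assumed) and the average rate is unchanged. At 5% on average, each factor is missing in 25% of that group, so 300 × (0.8 + 0.2 × 0.75^9) = 244 patients remain and power is about 65%. At 10%, 300 × (0.8 + 0.2 × 0.5^9) = 240 remain, with power about 65-67%. If missingness overlaps fully at 10%, 270 remain and power is 69%.

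**6. What imputation recovers.** Simulating multiple imputation with odds ratio 2.5 and 5% missing gives 72% against 56% complete-case (nine factors), and 69% against 60% (six factors). The difference between 72% and 69% is of the order of simulation error. Most of the loss returns, but not all.

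**The case against.** The study is declared exploratory, with no formal hypotheses, and its size is justified only by interval width. The predictor models are supplementary, so a power argument is not the plan's own yardstick. This stands as a limit on weight. It does not explain why the SAP withdraws work that the protocol promised, or why known outcomes should be discarded from a model that uses a P-value rule to find predictors.

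A reader might infer that power to find a real predictor will fall sharply. The documents do not support that as a fact, for these reasons:
- They give no missing rate, and at 1-2% per factor the loss is only about 4 to 9 points.
- Nine incomplete factors is close to a worst case. Age is needed for eligibility, chemotherapy is an entry condition, and sex is rarely unknown.
- ECOG, Ann Arbor and FLIPI are marked for both the enrolment visit and retrospective collection in Protocol Appendix 2, although pre-treatment values still come from records.
- Protocol 6.6.3 provides source data verification of critical data.

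A reader might also infer that poorly documented sites vanish as a block. That is an extreme case, and it cannot be combined with the independent-missingness figures: missingness that differs by site, as Protocol 6.7 expects, tends to overlap within patients and costs less.

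**Conclusion.** The inconsistency holds whatever the missing rate: Protocol 6.7.1 promises an examination of missing data and a justified covariate list, and the SAP delivers neither. The default consequence is complete-case deletion in the multivariable logistic and Cox models. The headline POD24 rate is untouched, and the chi-square tests are affected only factor by factor.

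The size is conditional. With an odds ratio of 2.5 and independent missingness in six to nine factors, all assumed, the loss from about 75% power is some 4 to 8 points at 2% missing, 15 to 19 at 5% and 24 to 39 at 10%. It is smaller if missingness clusters. No corresponding figure was worked out for the Cox models.

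This merits an SAP change, but it does not threaten the main result. It would be wrong to conclude that imputation makes the predictor model sound: about 4 events per candidate factor is thin for backward selection even with complete data.

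**What to change.** Amend SAP 3.6 so that outcomes are not imputed, but missing baseline covariates in the multivariable logistic and Cox models are multiply imputed:
- use chained equations containing all candidate factors, site type or region, and the outcome (event indicator and cumulative hazard for Cox);
- pool by Rubin's rules and apply factor removal to pooled Wald tests.

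Amend SAP 3.4 to report the complete-case model as a sensitivity analysis. Tabulate, by site, the patients and events missing each factor. In SAP 3.2, fix and justify the covariate list, as Protocol 6.7.1 requires, and state the analysis set for each model.

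The cost is SAP wording, standard R code and more analysis work, with no new data collection. A missing-at-random assumption must be stated. If little proves to be missing, the two models should agree closely. The shortage of events per factor remains and should be acknowledged when the models are reported.
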